5 STUDY PROCEDURES

	Pre-treat	Day of F18-EF5 PET/CT Prior to injection	Weekly during RT	Visit prior to surgery	30 days post surg/RT ^{1*}	Q3 months for 2 years, then q6 months for years 3 - 5 after surgery/RT	Yearly (as long as the patient wishes to be followed)
Tests and Observations							
History and PE	X		X	X	X	X	X
ECOG PS	X						
Biopsy	X						
Urine Pregnancy Test		X ²					
Toxicity Assessment	X		X			X	
Tumor Measurement	X ¹			X		X	
18F-EF5 PET Scan (optional)	X ³						

1- *Post radiation/surgery follow-up schedule defined for each cohort in Section 6.

2- Urine pregnancy test is routinely performed prior to PET/CT scanning as departmental standard.

3 – Subjects may participate in study with or without performing 18F EF5 PET scan. This is a subject option.

Post-treatment Evaluation and follow-up

All subjects will be evaluated prior to initiation of treatment and weekly during the course of radiotherapy. For patients receiving pre-operative radiation, a visit will occur prior to surgery. This visit will involve an interval history and physical. All patients will be seen for a first post-operative/post-radiation office visit with either the attending radiation oncologist or surgeon no more than 30 days following surgery/radiotherapy or discharge from the hospital, whichever comes later. Pre-operative patients will be seen after surgery, weekly x 1 month, then every 2nd week x 1 month, then monthly for 3 months. Post-operative patients will be seen one month after surgery and then in 3 months. Follow up visits for pre-operative and post-operative patients will be with either the attending surgeon or radiation oncologist every 3 months for two years, and every 6 months thereafter for 3 years. These office follow-up visits will consist of an interval history and physical and imaging studies as clinically indicated. The wound complication endpoint will be scored at 4 months after surgery in the pre-operative group. Post-operative patients will be scored for fibrosis, edema and joint stiffness within 2 years after after radiation.

Assessment of Tumor Response

Tumor Response (RECIST criteria): RECIST criteria will only be evaluated after radiation just prior to surgery in the pre-operative patients. Post-operative patients will not be evaluated since they undergo complete resection of STS.

Target Lesions:

- **Complete Response (CR):** Disappearance of all target lesions.

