For TOF reconstruction, we use the list-mode reconstruction implemented by Philips that is based upon a TOF list-mode maximum-likelihood algorithm which was originally developed in our laboratory at the University of Pennsylvania (45). This algorithm models data corrections in the algorithm and uses consecutively ordered subsets to accelerate the reconstruction. The Poisson statistics of the data are preserved by using the data in their original form (i.e., without binning) and incorporate the physical effects of PET imaging in the system model. The TOF kernel is modeled as a one-dimensional Gaussian function along the LOR and is applied in both the forward-projection and back-projection operations. We reconstruct patient studies using the protocol defined at the University of Pennsylvania that uses unrelaxed OSEM ($\lambda=1$) with 33 subsets and stops after three iterations for practical reconstruction time. A fully 3D list-mode iterative reconstruction algorithm is computationally intensive and required specialize computer equipment and software development to implement in practice. Using a 10-node (dual CPU) computer cluster, the image processing with this algorithm proceeds in parallel with data acquisition and is typically completed for clinical whole-body (multi-bed) studies 10-30 minutes after the end of the acquisition, depending on the number of counts collected.

The data corrections and 3D reconstruction that have been described help to improve the accuracy of quantification of the studies, in particular tumor contrast. Nevertheless, we do not expect that full recovery of contrast of small tumors will be achieved. Typically this is possible only if the tumor size is large compared to the spatial resolution. For example, the contrast of a 2-cm tumor is only about 50% of its true value, assuming that the region-of-interest is equal to the size of the tumor. Our image reconstruction algorithm has the capability of incorporating the measured point spread function into the system model so that we can recover the spatial resolution loss that is more significant as the distance from the center of the field-of-view increases. The resolution recovery technique will be further developed and validated for the tumor studies that will be performed for this project.

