Image registration of the PET images with other modalities (CT or MRI) will be performed using a mutual information algorithm developed at PENN and similar to the approach of Mattes (46). Our algorithm allows non-rigid, as well as rigid registration, using a set of user-defined correspondence points as constraints. For intra-patient comparisons between the PET scans and the MRI or CT, the fully automated rigid registration is expected to have sufficient accuracy.

Tumor ROIs will be drawn with the help of MRI and/or CT images. Tumor to normal tissue ratio will be determined in each voxel of the ROI.

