The relationship between pre-treatment hypoxia as determined by F18-EF5 scanning and treatment outcome will be examined, stratified by pre- and post-operative cohorts. The clinical outcomes are: RECIST response rate (pre-operative patients only), time to local recurrence, time to distant recurrence, PFS and OS. We hypothesize that high ¹⁸F-EF5 signal of the primary tumor (e.g. high levels of hypoxia) will relate to poorer clinical outcome (lower response rate, shorter time to local recurrence, shorter time to distant recurrence, shorter PFS, and shorter OS) in this group of patients. We will examine the prognostic values of hypoxia, as measured by ¹⁸F-EF5, summarized from regions of the primary tumors. These analyses will be stratified by pre- or post-operative cohorts. Each subject will have summary statistics for hypoxia using ¹⁸F-EF5 PET available from the primary tumor for this analysis. The Kaplan-Meier method will be applied to estimate the distribution of time-to-event outcome variables for patients with ¹⁸F-EF signal above or below median of the summarized values. The association between RECIST response and hypoxia (binary coding) will be assessed by chi-square test. The association between time-to-event outcomes and hypoxia will be established by the Cox proportional hazards models. Both binary and continuous summary measures of ¹⁸F-EF5 signal will be evaluated. A binary indicator for a hypoxic tumor can be defined as ¹⁸F-EF5 signal above versus below median signal or based on other previously defined cut points. The direction and magnitude of the association will be assessed by hazard ratio and its 95% confidence interval.

6.4 SAMPLE SIZE/POWER AND TRIAL DURATION.

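### The exploratory EF5-outcome analyses carry no tumour-size term, although the protocol says PET contrast is under-recovered in small tumours; a size-adjusted estimate should be reported beside the unadjusted one

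*Combined protocol and SAP*

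**What the plan says.** Section 5, under PET scan imaging and analysis, describes the corrections and reconstruction and then gives a limit: "we do not expect that full recovery of contrast of small tumors will be achieved". On full recovery it adds: "Typically this is possible only if the tumor size is large compared to the spatial resolution". Its worked example is that "the contrast of a 2-cm tumor is only about 50% of its true value", with the condition "assuming that the region-of-interest is equal to the size of the tumor". The mitigation offered is point-spread modelling: "The resolution recovery technique will be further developed and validated for the tumor studies that will be performed for this project".

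The hypoxia measure is set in the same subsection: "Tumor to normal tissue ratio will be determined in each voxel of the ROI". No partial-volume or size correction of that ratio is described.

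Section 6.3, under the exploratory EF5 analyses, reduces each tumour to summary statistics without saying which (mean, maximum, or fraction above a cut point). It splits patients at the median, allows other cut points and a continuous version, and hypothesises that high signal goes with poorer outcome. RECIST response is tested by chi-square. For the other outcomes: "The association between time-to-event outcomes and hypoxia will be established by the Cox proportional hazards models". The only control named is cohort.

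The study procedures table in section 5 has a "Tumor Measurement" row with a pre-treatment entry. Section 6.4 declares all the hypoxia analyses exploratory, but says they will estimate the size of the associations and guide future studies.

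**The concern.** By the protocol's own account, two equally hypoxic tumours of different size can give different EF5 readings, with the smaller one reading lower. A median split on the measured ratio then sorts patients partly by size. If larger tumours also do worse, size raises both the signal and the hazard, and it does so in the direction of the stated hypothesis. An unadjusted hazard ratio above 1 could then be read as a hypoxia effect when some or all of it is a size effect. The hazard ratio with its 95% confidence interval is the stated output of this objective, and later studies are meant to use it.

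**Working it through.** **Inputs from the protocol.** Contrast recovery is about 50% at 2 cm for a tumour-sized region (section 5). There are up to 40 evaluable patients per cohort (section 6.2), and the scan is optional (section 5 table). The split is at the median (section 6.3). Local control is 90% or greater with surgery and radiotherapy (Introduction).

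**Assumptions not in the protocol.** Median diameter 5 or 8 cm, log-SD 0.6. True tumour-to-normal excess with log-SD 0.2 or 0.4, independent of size. Hazard ratio per doubling of size 1.0, 1.5 or 2.0. About 14 events in 40 patients.

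**Step 1: recovery by size.** The 50% figure cannot be derived independently, because the scanner resolution is not given. It was used to calibrate a uniform sphere blurred by a Gaussian; mean recovery of 0.50 at 2 cm needs a FWHM of 1.05 cm. Mean recovery is then 0.65 at 3 cm, 0.79 at 5 cm, 0.87 at 8 cm, 0.89 at 10 cm and 0.93 at 15 cm. Recovery at the central voxel is 0.83 at 2 cm and 0.99 at 3 cm.

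Measured ratio = 1 + (true ratio − 1) × recovery. A true ratio of 2.0 reads 1 + 1 × 0.50 = 1.50 at 2 cm and 1 + 1 × 0.89 = 1.89 at 10 cm.

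**Step 2: effect on the hazard ratio.** Cox models were simulated with no true hypoxia effect, a whole-tumour mean split at the median, n = 40 and 600 runs per row. The rates are false positives at two-sided 5%.

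| Excess log-SD | Median cm | Size HR | HR, no size term | HR, log2 size added | Rate, no size term | Rate, size added |
|---|---|---|---|---|---|---|
| 0.4 | 5 | 1.5 | 1.30 | 1.07 | 5.8% | 5.0% |
| 0.4 | 5 | 2.0 | 1.37 | 0.99 | 7.5% | 4.7% |
| 0.4 | 8 | 1.5 | 1.16 | 1.02 | 5.0% | 4.2% |
| 0.4 | 8 | 2.0 | 1.25 | 1.01 | 5.3% | 4.2% |
| 0.2 | 5 | 1.5 | 1.37 | 1.00 | 7.8% | 4.7% |
| 0.2 | 5 | 2.0 | 1.76 | 0.99 | 13.5% | 4.5% |
| 0.2 | 8 | 1.5 | 1.22 | 1.00 | 5.3% | 3.8% |
| 0.2 | 8 | 2.0 | 1.53 | 1.02 | 9.0% | 5.7% |

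Simulation error on a log hazard ratio is about 1.253 × 0.53 / √600 = 0.027. On a 5% rate it is √(0.05 × 0.95 / 600) = 0.9 percentage points. Rates near 5 to 6% are therefore not distinguishable from nominal.

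**Step 3: when the bias goes away.** With a size hazard ratio of 1.0, the unadjusted hazard ratio is 0.97 to 1.04. With a noise-free peak-voxel summary and excess log-SD 0.4, it is 1.00 to 1.09.

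**Step 4: against sampling error.** With 14 events split evenly, SE(log HR) ≈ √(4/14) = 0.53. The 95% interval spans a factor of exp(1.96 × 0.53) ≈ 2.8 to 2.9 either way. A bias of 1.1 to 1.4 is ln(1.1)/0.53 = 0.18 to ln(1.4)/0.53 = 0.63 standard errors.

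**Step 5: local recurrence.** Local control of 90% or greater implies at most about 0.10 × 40 = 4 local failures per cohort, too few for a useful two-covariate Cox model.

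**The case against.** The 50% figure holds only for a region equal to the tumour, while the ratio is computed voxel by voxel and the summary is left open. A peak-type summary would largely escape the problem. The protocol does not say that larger tumours do worse, and it gives no size mix. It discloses the recovery limit, names a mitigation and labels the analyses exploratory. No primary endpoint, sample size or stopping rule depends on them, and at this sample size random error exceeds the bias. All of this stands, and it makes the point conditional and modest. It does not remove the point: nothing in section 6.3 selects the less affected summary or ties the analysis to the mitigation, and exploratory status excuses low power better than it excuses a foreseeable bias.

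Three stronger readings are tempting.

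- A reader might infer that early and late scans will be reconstructed with different recovery versions and then share one median. Section 5 says the technique will be developed and validated for the project's tumour studies. It does not say that versions will be mixed, and it states fixed reconstruction settings.
- A reader might quote larger biases, 1.32 to 1.71, which appear in a similar large-sample simulation if true hypoxia correlates 0.3 with size. Part of that is ordinary confounding by size, not the recovery loss the protocol describes, and the protocol gives no such correlation.
- A reader might want the adjusted hazard ratio to become the main estimate in every model. Step 5 shows why that fails for local recurrence. The simulations also test only the null, so they do not show that adjustment recovers a real hypoxia effect.

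**Conclusion.** The point holds in a limited form. The signal depends on tumour size by the protocol's own statement, and no size term is planned. For a whole-tumour mean, with hazard rising 1.5- to 2.0-fold per doubling of size and excess log-SD 0.4, the unadjusted hazard ratio can be about 1.1 to 1.4 with no true effect. It returns close to 1 when log size is added. A narrower spread of true hypoxia (log-SD 0.2) raises the upper end to 1.76; mostly large tumours lower it. The bias is small for a peak-voxel summary and absent if size does not affect outcome. At about 40 patients per cohort the harm is mainly a shifted estimate, since with log-SD 0.4 the false-positive rate is only 5.0 to 7.5%. The protocol does not support saying that the planned analysis will report a size effect as hypoxia, only that it could not tell the two apart.

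**What to change.** Amend the EF5 part of section 6.3 as follows.

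- Keep the unadjusted analyses. Beside them, report a hazard ratio adjusted for log baseline longest diameter for PFS, OS and time to distant recurrence, where the number of events allows.
- For RECIST response, add a size-adjusted logistic estimate beside the chi-square test, where the number of responses allows.
- Report the correlation of the EF5 summary with tumour size, naming the summary used.
- State that an unadjusted association that disappears on adjustment will not be interpreted as a hypoxia effect.
- Do not require adjustment for time to local recurrence.

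The cost is a few sentences and minor analysis work, using the baseline measurement already scheduled. Adjustment uses one more degree of freedom and widens intervals slightly. If larger tumours are truly more hypoxic, it may also absorb some real signal, which is why both estimates should be shown.

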6 STATISTICAL PLAN

This is a study of proton therapy in extremity soft tissue sarcoma (STS). Patients will be stratified into pre- and post-operative cohorts. The trial will be conducted in two phases, first, a feasibility study and then, a phase II study to detect reduced complication rates. Since proton is a new treatment modality at PENN, the first proton trial conducted in each cancer site will be a feasibility study, in order to gain experience on both the logistics of proton planning, dosimetry, scheduling and delivery and patient safety issues.

6.1 FEASIBILITY STUDY.

Design and Objectives:

This feasibility trial is designed to establish feasibility and safety of proton therapy. Patients are stratified into pre-operative and post-operative groups with 12 patients in each stratum. Patients with STS of the upper or lower extremity will be treated in the feasibility study. These cohorts will be accrued, evaluated and advanced to the second phase independently. Patients enrolled in the

CONFIDENTIAL

feasibility study will continue to be followed for secondary endpoints, such as late toxicity and clinical efficacy.

Pre-operative patients will receive 5-6 weeks of radiation. Four to 12 weeks after completion of radiotherapy they will undergo surgery. In the feasibility study, pre-operative patients will be followed for a minimum of 90 days after start of radiation treatment or 30 days after surgery, whichever comes later to determine feasibility and safety (acute toxicity) before moving to the second phase of the study.

Post-operative patients will receive 8 weeks of radiation. Four weeks after completion of radiotherapy patients may receive chemotherapy, if clinically indicated. Post-operative patients will be followed for a minimum of 90 days after start of radiation treatment, to determine feasibility and safety (acute toxicity) before moving to the second phase of the study. Toxicities experienced during the post-radiation follow-up window will be carefully evaluated for relatedness to proton therapy or to surgery or chemotherapy.

Endpoints

Primary Endpoints:

(i) **Feasibility** will be based on multiple radiation planning and treatment parameters. Should a patient experience one of the following events, treatment will be deemed infeasible:

Patient cannot be given treatment because anatomy is such that a dosimetrically satisfactory treatment plan cannot be devised. For example, the dosimetry is unsatisfactory if <95% of target volume is covered by 95% of the dose.

Patient is unable to tolerate 25% of treatments using proton radiotherapy, that is, up to 25% of treatments could be delivered using photons. Reasons for missed treatments may include: unable to set patient up within acceptable limits of tolerance, patient unable to tolerate treatment position or immobilization for duration of treatment).

Patient is unable to complete all of his/her treatments within 10 days of estimated date of treatment completion or requires a treatment break greater than 5 days.

(ii) **Acute toxicity** is defined as any grade 3 or higher hematologic or non-hematologic toxicity that is probably or definitely related to radiotherapy (not surgery). All toxicities observed within 90 days from start of radiotherapy, will be graded by NCI CTC Version 4.0. For pre-operative patients all toxicities observed within 90 days after start of radiation treatment or 30 days after surgery, whichever comes later, will be graded.

Secondary Endpoints:

(i) **Late toxicity** is defined as any grade 3 or higher hematologic or non-hematologic toxicity which occurs after 90 days from start of therapy. Late toxicities will be graded according to the RTOG/EORTC late toxicity criteria. The time frame for late toxicity is open-ended and late toxicities have been known to occur a year or more after therapy. Follow-up for late toxicity will cease when a patient experiences disease progression, since 2nd line therapies may then be initiated.

(ii) **Wound complication** is defined as a secondary operation under general or regional anesthesia for wound repair or wound management without second operation. Wound management includes an invasive procedure without general or regional anesthesia, readmission for wound care such as iv antibiotics, or persistent deep packing for 120 days or longer. Patients will be assessed for wound complications which develop within 4 months after surgery.

(iii) **Fibrosis and joint stiffness** will be graded according to EORTC/RTOG late radiation toxicity criteria. **Edema** will be graded as 0= none, 1= mild, 2= moderate, 3= severe, 4= very severe, according to the criteria of Stern (Stern TN. Clinical examination: a textbook. Year Book Medical

CONFIDENTIAL

Publishers, 1964). Patients will be assessed for fibrosis, joint stiffness and edema within 2 years of completion of radiotherapy.

Clinical Efficacy is defined for pre-operative patients as overall response rate (CR + PR according to RECIST criteria) which is scored after radiation and before surgery. Progression-Free Survival is defined from first day of treatment to first documented failure, death due to any cause or last patient contact alive. Overall Survival is defined from first day of treatment until death due to any cause or last patient contact alive. Time to local failure, time to distant failure, PFS and OS will be calculated from first day of radiation in the pre-operative patients and calculated from day of surgery in the post-operative patients.

Rules for Early Termination for Feasibility, Acute Toxicity and Wound Complication:

Bayesian probability calculations will be employed to define rules of early termination and end of trial evaluation for feasibility and safety. The tables below indicate termination rules after groups of 3 patients have been treated. Hundreds of patients with certain types of cancer have undergone radiation therapy with protons. Thus, we will assume some "prior" feasibility and safety data for protons delivered at the standard radiation dose for our Bayesian calculations. We will assume prior information equivalent to that of 6 treated patients, which is commonly required to establish feasibility and safety in a standard 3+3 phase I trial design.

Feasibility – conducted separately for each stratum

We will assume a beta (5,1) prior, which is information equivalent to feasibility established in 5 of 6 treated patients. A feasibility rate > 90% is considered acceptable. If the number of patients deemed feasible is less than or equal to the number in the table below then termination will be considered as it is highly unlikely that the feasibility rate is > 90%, as noted by the Bayesian posterior probabilities.

Bayesian Rule for Feasibility				
Patients treated	3	6	9	12
Patients who are feasible	1	4	6	9
Posterior Prob[feasibility rate >90%]	0.0	0.0	0.0	0.0
Action	Terminate enrollment			

Acute Toxicity – conducted separately for each stratum * excludes wound complication *

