- To determine the acute and late toxicities of proton radiotherapy to the extremities.
- To monitor for effects of proton treatment on tumor and normal tissues using radiographic imaging (both cohorts) or *ex-vivo* analysis of tissue samples (pre-operative cohort only).
- To examine the relationship between pre-treatment hypoxia as determined by F18-EF5 scanning and treatment outcome.

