4 SURGERY , CHEMOTHERAPY AND IMAGING

Radiation therapy will be performed either preoperatively or postoperatively. This decision will be made by the attending surgeon and radiation oncologist. For patients in the preoperative cohort, surgery will be performed 4-12 weeks after completion of radiotherapy. This will consist of resection of all gross tumor with adequate margins, sampling of lymph nodes and any other areas suspicious for involvement by the sarcoma as clinically appropriate. For patients in the postoperative cohort, radiotherapy will begin 3-8 weeks following surgery.

Chemotherapy (standard of care as determined by medical oncology) may be given no sooner than day 30 after radiation therapy for the post-operative patients or day 30 after surgery if radiotherapy is pre-operative as deemed clinically appropriate by the attending surgeon and radiation oncologist.

CONFIDENTIAL

18F-EF5 PET Scan

Up to 4 weeks prior to treatment with either surgery or proton radiation, ^{18}F -EF5 will be administered in the Department of Nuclear Medicine in the Hospital of the University of Pennsylvania (HUP) or in the Department of Radiation Oncology in the Perelman Center for Advanced Medicine. Approximately 5mCi of ^{18}F -EF5 will be administered as an IV bolus (for details of ^{18}F -EF5 synthesis, see specific methods, below). After the injection of ^{18}F -EF5, subjects will be asked to remain in the Nuclear Medicine or Radiation Oncology waiting room during the free time before their PET/CT scan, where they may relax until they are required to go to the PET/CT scan room. There is no bathroom restriction during this time. The Scan will be performed at 180 minutes (evaluation of hypoxia) following injection. Subjects will be positioned on the PET-CT imaging bed comfortably with their head secured in the head hold of the PET instrument.

TIME (APPROXIMATELY)	SCHEDULE OF EVENTS
-30 minutes	Transport to nuclear medicine facility
-10 minutes	Placement of one intravenous line
0 minutes	Injection of ^{18}F -EF5 (\approx 5 mCi)
1-179 minutes	Free time
180 minutes	PET/CT Scan
215 minutes	Study completed

Table 3: ^{18}F -EF5 PET Protocol**Expected Adverse Events Associated with radioactive ^{18}F -EF5.**

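### Late toxicity lacks the radiotherapy-relatedness criterion used for acute toxicity, although its window holds chemotherapy and surgical recovery and overlaps the acute window

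*Combined protocol and SAP*

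**What the plan says.** Section 6.1 (Endpoints) defines the two toxicity endpoints one after the other. Acute toxicity is a grade 3 or higher event "that is probably or definitely related to radiotherapy (not surgery". It is graded by CTC version 4.0 up to day 90 from the start of radiotherapy; in pre-operative patients grading runs to 30 days after surgery if that is later. Late toxicity "is defined as any grade 3 or higher hematologic or non-hematologic toxicity which occurs after 90 days from start of therapy". It is graded on the RTOG/EORTC late scale, and its follow-up ends at progression because second-line treatment may then begin.

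The analysis text in 6.1 tabulates late toxicities as previously defined, and 6.3 tabulates them by stratum. Neither splits them by cause. The objective being served, in Section 1, is "To determine the acute and late toxicities of proton radiotherapy to the extremities".

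Three other places bear on this:
- Section 4: chemotherapy "may be given no sooner than day 30 after radiation therapy for the post-operative patients or day 30 after surgery" where radiotherapy came first.
- Section 6.1 (Design and Objectives), at the end of the post-operative paragraph: "Toxicities experienced during the post-radiation follow-up window will be carefully evaluated for relatedness to proton therapy or to surgery or chemotherapy".
- Section 7 (Radiation Effect): late effects are those more than 3 months after radiation, evaluated on the RTOG/EORTC late radiation morbidity system.

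**The concern.** The trial's case for protons is lower short- and long-term morbidity, so its late-toxicity table will be read as the late harm of proton radiotherapy. As worded, the endpoint takes in every grade 3 or higher event after day 90, and hematologic events are named explicitly. If other treatments are given mainly after day 90, their toxicity enters the count. The rate would then depend partly on how many patients receive chemotherapy and on how surgical recovery goes, and it would not be on the same basis as the acute rate reported beside it. Overlapping windows would also allow one event to be counted as both acute and late.

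**Working it through.** The plan states no rate, threshold or power for late toxicity, so there is no figure to reproduce. The check is whether the schedule puts other treatments in the late window. Days are counted from the first day of radiation.

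**Inputs.** Pre-operative radiation R = 5 to 6 weeks (6.1: "Pre-operative patients will receive 5-6 weeks of radiation"); gap to surgery G = 4 to 12 weeks (6.1 and Section 4); post-operative radiation 8 weeks, or 56 days (6.1); earliest chemotherapy 30 days after surgery (pre-operative) or after radiation (post-operative) in Section 4. For post-operative patients 6.1 gives four weeks (28 days) instead, so both values are carried.

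**Pre-operative cohort.** Surgery day S = 7 × (R + G). Acute window end = max(90, S + 30). Earliest chemotherapy = S + 30. Overlap = acute window end − 90.

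| R (weeks) | G (weeks) | Surgery day | Acute window ends | Earliest chemotherapy | Overlap (days) |
|---|---|---|---|---|---|
| 5 | 4 | 63 | 93 | 93 | 3 |
| 5 | 12 | 119 | 149 | 149 | 59 |
| 6 | 4 | 70 | 100 | 100 | 10 |
| 6 | 12 | 126 | 156 | 156 | 66 |

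- All permitted chemotherapy starts after day 90.
- Surgery itself falls after day 90 once G exceeds (90 − 42)/7 = 6.9 weeks with 6 weeks of radiation, or (90 − 35)/7 = 7.9 weeks with 5.
- Taking 4 months as 122 days, the wound-complication window after the earliest surgery ends on day 63 + 122 = 185, so (185 − 90)/122 = 78% of it lies after day 90. If surgery is on day 90 or later, all of it does.
- In the overlap, a radiotherapy-related grade 3 or higher event meets both definitions, on two grading scales.

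**Post-operative cohort.** Earliest chemotherapy is day 56 + 28 = 84 or 56 + 30 = 86, so at most its first 4 to 6 days precede day 90.

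**Section 7 boundary.** Taking 3 months as 90 days, late effects begin after day 35 + 90 = 125 to 42 + 90 = 132 (pre-operative) or day 56 + 90 = 146 (post-operative), not after day 90. A post-operative event between day 91 and day 146 is late under 6.1 and acute under Section 7.

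***Start of therapy*.** The late definition does not say which therapy. In the post-operative cohort survival times run from surgery, and Section 4 starts radiation 3 to 8 weeks (21 to 56 days) later. If the late window also ran from surgery, its day 90 would be radiation day 90 − 21 = 69 down to 90 − 56 = 34. The latter lies inside the 56-day radiation course.

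**Relatedness review.** Its sentence closes a paragraph on the minimum 90-day follow-up of post-operative patients. On a narrow reading it covers that cohort from about day 56 to day 90. It names three possible causes but no attribution categories, and neither the late definition nor its tabulation refers to it.

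**The case against.** A reader might infer that late toxicity has no link to radiotherapy at all, or that the trial cannot isolate late proton toxicity. The documents do not support either reading. Section 6.1 promises a relatedness review. Late events are graded on a scale made for radiation morbidity, and Section 7 sends adverse events other than late radiation effects to CTCAE. On that reading a chemotherapy cytopenia after day 90 would be an ordinary adverse event. Follow-up also stops at progression, which keeps second-line treatment out. If attribution is recorded, related late events can be separated at analysis.

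This removes the strong claim but leaves the gap. A scale sets the grade, not the cause; the acute endpoint has a scale too and still adds an attribution test. The explicit inclusion of hematologic events pulls against the Section 7 reading. Stopping at progression does not remove surgery or chemotherapy given before it.

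It is also fair to say that all-cause counting is a legitimate, cautious choice in a single-arm trial. The introduction attributes fracture, lymphedema and soft-tissue damage to surgery and radiation in combination. An attributed rate alone, or one with wound complications removed, could hide radiation-related harm. That stands, and it argues for showing both counts. Nor did the late endpoint lose a wound exclusion: that exclusion is a note on the acute stopping rule, not part of the acute definition.

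**Conclusion.** As defined and tabulated, the late-toxicity rate does not separate late proton toxicity from chemotherapy or surgical toxicity. The timing follows from the protocol's own schedule, taking *start of therapy* as the first day of radiation and the 6.1 durations as typical. The 3 to 66 day overlap and the differing Section 7 boundary are further inconsistencies in the text.

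The size of the contamination cannot be given. The documents state neither how many patients will receive chemotherapy nor how often it causes grade 3 or higher events, so any percentage would reflect only the inputs chosen. A reader might be tempted to add the 43% wound-complication rate (30 of 70 lower-extremity photon patients, Section 6.2). That figure is not broken down by grade or by whether events came after day 90, so it does not measure this effect.

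The consequence is limited to how the late-toxicity table can be read. Late toxicity is a descriptive secondary endpoint with no test or stopping rule. Power and the primary analyses, including the separately defined fibrosis endpoint, are unaffected.

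**What to change.** 1. In 6.1, state that the relatedness review applies to late events in both cohorts, and name the attribution categories.
2. In 6.1 and 6.3, tabulate late grade 3 or higher events twice: all-cause, and probably or definitely related to radiotherapy. Flag events that are also scored as wound complications; do not drop them.
3. Reconcile the acute/late boundary in 6.1 with Section 7, including the pre-operative extension to 30 days after surgery, and define *start of therapy* for each cohort, so that each event is counted once.

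The cost is wording and an extra table line, with attribution recorded for late events where it is not already. No patients or visits are added, since Section 5 already schedules toxicity assessment at the follow-up visits. The small downside is that attribution is a judgement; the all-cause line covers that.
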